1.2 ENDPOINTS

1.2.1 PRIMARY

Safety endpoints will be the solicited AE (local and systemic reactogenicity), and related AEs and SAEs.

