7.2 ANALYSIS

7.2.1 POWER AND SAMPLE SIZE

The safety, reactogenicity, and tolerability of the vaccine regimens are the primary endpoints for this study. Below in Table 6, the estimated probability of a participant having at least one of these events (in percent), along with the associated exact Clopper-Pearson 95% confidence interval, is given for various numbers of observed events that correspond to approximate event rates within study groups of possible interest. Note that some event rates cannot be exactly observed within a given group, depending on the sample size (e.g. 10% of 15 participants is 1.5 participants, which is rounded to 2 in the table below).

Table 5: Estimated probability (in percent) of a participant having at least one AE, along with the associated exact Clopper-Pearson 95% CI, given varying sample sizes and numbers of participants with at least one observed AE

Group	n	Approximate AE Rate ¹							
		0%		10%		20%		50%	
		Corresponding # AEs ²	Estimated Probability (95% CI)	Corresponding # AEs ²	Estimated Probability (95% CI)	Corresponding # AEs ²	Estimated Probability (95% CI)	Corresponding # AEs ²	Estimated Probability (95% CI)
Each Individual Group	15	0	0 (0, 21.8)	2	13.3 (1.7, 40.5)	3	20 (4.3, 48.1)	8	53.3 (26.6, 78.7)
Placebo	21	0	0 (0, 16.1)	2	9.5 (1.2, 30.4)	4	19 (5.4, 41.9)	11	52.4 (29.8, 74.3)
Any DNA Prime with HIV Env gp145 C.6980 /Rehydragel Boosts	105	0	0 (0, 3.5)	11	10.5 (5.3, 18.0)	21	20 (12.8, 28.9)	53	50.5 (40.5, 60.4)
DNA alone (1+2), DNA+TCI (3+4), DNA/ALF43 (5+6)	30	0	0 (0, 11.6)	3	10 (2.1, 26.5)	6	20 (7.7, 38.6)	15	50 (31.3, 68.7)
HIV Env gp145 C.6980 /Rehydragel boost (1+3+5), HIV Env gp145 C.6980 /Rehydragel/ALF43 boost (2+4+6)	45	0	0 (0, 7.9)	5	11.1 (3.7, 24.1)	9	20 (9.6, 34.6)	23	51.1 (35.8, 66.3)
Any ALF43	75	0	0 (0, 4.8)	8	10.7 (4.7, 20.0)	15	20 (11.6, 30.8)	38	50.7 (38.9, 62.4)

¹ The approximate proportion of participants in a group reporting at least one event of interest

² The number of participants with observed event(s) needed to most closely correspond to the given approximate event rate, with the given sample size

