8 SAFETY AND REPORTING

8.1 ASSESSING AND RECORDING SAFETY PARAMETERS

8.1.1 REACTOGENICITY

8.1.1.1 Diary Card (7-Day Solicited Reactogenicity)

Reactogenicity events are AEs that are common and known to occur following administration of this type of study vaccine. A diary card will be used to aid in the collection of potential reactions.

Temperature and solicited local and systemic symptoms will be recorded in the clinic before vaccination and 30-60 minutes post-injection, at home about 6 hours after vaccination, and then daily by the participant for 7 days. Solicited symptoms that persist after the end of day 7 will be considered an AE or SAE, will be documented, and followed through resolution.

At each vaccination visit, participants will be given a new diary card, a thermometer and a ruler. The diary card will be used as a memory aid, on which the participant will record oral temperature, local and systemic symptoms, and concomitant medications daily for 7 days, beginning with the day of vaccination. Participants will be trained to complete the diary card, how to use the thermometer, and how to measure injection site swelling and redness using the ruler after each vaccination. Completion of the diary card training will be noted in source documents. The diary card is not a source document; the information gained from the review of the diary card and the interview with participants will be documented using a combination of progress notes and CRFs maintained in the participants research chart.

The solicited signs and symptoms on the diary card are:

Local

- Pain/tenderness
- Itching
- Warmth
- Redness/erythema measurement of largest dimension
- Swelling/induration measurement of largest dimension

Systemic

- Fever
- Myalgia
- Arthralgia
- Headache
- Fatigue
- Chills
- Rash
- Nausea

- Dizziness

Where multiple assessments are taken on the same day, participants will be requested to record the day's highest measured temperature and measurement of largest dimension for redness and swelling.

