8.1.7 ADVERSE EVENT ASSESSMENT

All AEs (laboratory and clinical symptoms) will be graded for severity and assessed for relationship to study product using the DAIDS Table for Grading the Severity of Adult and Pediatric Adverse Events (DAIDS AE Grading Table), Version 2.1 dated July 2017 that is found on the website <https://rsc.niaid.nih.gov/clinical-research-sites/daids-adverse-event-grading-tables>. AEs characterized as intermittent require documentation of onset and duration of each episode.

The start and stop date of each reported AE will be recorded on the appropriate data collection form and eCRF. Changes in the severity of an AE will be documented to allow an assessment of the duration of the event at each level of intensity. Adverse events not identified in the grading table, follow the guidelines provided at the beginning of the table.

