APPENDIX I. DIARY CARD

LABEL

Diary Card

Participant ID: | 4 | 6 | 0 | - | | | | | |

Vacc. #: _____

Vaccination Date: _____

DD

MM

YYYY

Short title: Comparative Adjuvant Study for HIV-1 Env DNA and Protein Vaccines in Kenya
 RV460 / WRAIR #2672

13-07-2020
 Version 1.7

Instruction for recording No. 2-7 and 8-15

Please use the grading scale below to record the severity of your reaction to the injections in the next sections:

0 = None**1 = Mild:** minimal interference with usual social and functional activities.**2 = Moderate:** symptoms causing greater than minimal interference with usual social and functional activities.**3 = Severe:** symptoms causing inability to perform usual social and functional activities

Time After vaccination	30-60 min	6 hr	Day 1	Day 2	Day 3	Day 4	Day 5	Day 6	Day 7
Day/Month	__ / __	__ / __	__ / __	__ / __	__ / __	__ / __	__ / __	__ / __	__ / __
Time taken (hrs/min)									
1. Oral temperature (Celsius)									

Vaccination injection site reactions		 Right arm		 Left arm	
2. Injection site pain or tenderness					
3. Swelling (at injection site)					
4. Itching (at injection site)					
5. Redness (measure the largest dimension in cm.)					
6. Hardness (measure the largest dimension in cm.)					
7. Warmth (at injection site)					

General Reactions (not injection site)								
8. Headache								
9. Chills								
10. Dizziness								
11. Tiredness / Fatigue								
12. Nausea								
13. Muscle pain								
14. Joint pain								
15. Rash (if present, describe in "other symptoms")								
16. Took medication for fever or for above symptoms?	0=No 1=Yes							

Other symptoms (please describe):								

LABEL

Diary Card

Participant ID: | 4 | 6 | 0 | - | | | | |

Vacc. #: _____

Vaccination Date: _____

DD

MM

YYYY

Short title: Comparative Adjuvant Study for HIV-1 Env DNA and Protein Vaccines in Kenya
 RV460 / WRAIR #2672

13-07-2020
 Version 1.7

If you take any medication, please record in the table below
 If you take medications for fevers, please check your temperature again after 4 hours and record above in "Other symptoms"

Medication	Dose/route	Reason	Start date	Stop date

Suggestion

- Complete the diary card in as much detail as you can every day, at the same time each day
- Record any problems that occur during this period
- Bring back this diary card with you at the next appointment
- If you forget to record any data, leave it blank

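### The diary-card scale has no descriptor for a symptom that is present but hinders nothing, so some mild solicited reactions may be entered as 0

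*Protocol*

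**What the plan says.** Appendix I heads the scale "Instruction for recording No. 2-7 and 8-15", which covers the six local items and the eight general items, and introduces it with "Please use the grading scale below to record the severity of your reaction to the injections in the next sections". The levels are:

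- 0, labelled None, with no further description;
- 1, labelled Mild: "minimal interference with usual social and functional activities";
- 2, labelled Moderate: "symptoms causing greater than minimal interference with usual social and functional activities";
- 3, labelled Severe: inability to carry out those activities.

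Section 1.2.1 (repeated in 2.7.1) makes these reactions part of the primary endpoint: "Safety endpoints will be the solicited AE (local and systemic reactogenicity), and related AEs and SAEs". Section 7.2.2 tabulates reactogenicity by group with exact confidence intervals and reports each participant's maximum severity.

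Section 8.1.1.1 limits the role of the card: "The diary card is not a source document; the information gained from the review of the diary card and the interview with participants" go into progress notes and CRFs. A clinician reviews the card about day 7 after each dose. Section 8.1.7 sets the grading standard: "All AEs (laboratory and clinical symptoms) will be graded for severity and assessed for relationship to study product using the DAIDS Table". The protocol does not reproduce that table's definitions.

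**The concern.** Every non-zero level is described by interference with activities. A participant whose arm is slightly itchy or warm, and who is hindered in nothing, finds no descriptor that fits. The label Mild points to 1; the text beside it, read literally, points to 0.

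The ambiguity sits on the boundary between any and no reaction. Section 7.2.1 plans on the proportion of participants with at least one event, and section 7.2.2 estimates such proportions. A symptom entered as 0 and not picked up at review lowers that proportion. It also leaves no trace, because a 0 looks like a real observation of no symptom.

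The items most exposed are those without a measurement: itching, warmth and the general symptoms. Swelling is exposed too, because card item 3 carries no centimetre instruction although section 8.1.1.1 lists swelling/induration as a measured sign. Itching deserves attention here because section 2.2.3.5 describes this trial as the first to give dmLT by the transcutaneous route and lists pruritus among the known effects of LT patches.

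**Working it through.** **1. Does any descriptor cover the state?** Setting symptom status against the card:

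| Participant's state | By label | By descriptor |
|---|---|---|
| No symptom | 0 | 0 |
| Symptom, no interference | 1 (Mild) | none fits; 0 is possible |
| Symptom, minimal interference | 1 | 1 |
| Symptom, more than minimal interference | 2 | 2 |
| Symptom, unable to perform activities | 3 | 3 |

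Only the second row is unresolved, and it decides between any and none.

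**2. Would a wrong 0 be caught?**

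- Section 8.1.1.1 requires recall when information is missing or the card is lost. An entered 0 is neither. The card tells participants to leave forgotten items blank.
- The Appendix Q telephone script, which staff may use as guidance, offers two alternative follow-up prompts: one asks about complaints, the other whether daily activities are possible without a problem. The second repeats the interference criterion.
- The clinic check at 30-60 minutes precedes later reactions; section 2.2.3.1 reports recall reactions in a predecessor trial at 36 to 72 hours.
- Appendix A has a day-3 visit after vaccinations 1, 3, 4 and 6. After vaccinations 2 (day 28) and 5 (day 224) the next scheduled visits are days 35 and 231, so days 1 to 6 rest on the card, the early telephone or clinic contact, and recall.

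These steps lower the chance of a lasting wrong 0. None is stated as a check on zeros.

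**3. Size, as illustration only.** Let p be the true proportion of reactors and s the share of them recorded as having no reaction at any time point, with no correction at review. The documents give no value for s; 0 to 50% is assumed. The recorded rate is r = p × (1 − s), and in a group of 15

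P(at least 2 recorded) = 1 − (1 − r)^15 − 15 × r × (1 − r)^14.

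With p = 20% and s = 0 this is 1 − 0.0352 − 0.1319 = 83.3%, which reproduces the protocol's Table 6 entry for an individual vaccine group.

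| s | r when p = 20% | P(at least 2 of 15) | r when p = 53.3% (8/15) |
|---|---|---|---|
| 0 | 20% | 83.3% | 53.3% |
| 10% | 18% | 78.1% | 48.0% |
| 25% | 15% | 68.1% | 40.0% |
| 50% | 10% | 45.1% | 26.7% |

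In the terms of Table 5, 8 of 15 gives 53.3% (26.6 to 78.7), which also reproduces. Recording 6 of 15 (8 × 0.75) would give 40.0% (16.3 to 67.7), and 4 of 15 (8 × 0.50) would give 26.7% (7.8 to 55.1).

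**The case against.** The strongest reply is that few participants would read the card that way. It asks for the severity of a reaction; someone with an itchy arm has a reaction, so None is false and Mild fits. Because level 2 begins above minimal interference, level 1 can be read as everything present below that. The rash item asks for a description if a rash is present, and the card separately asks participants to record any problems. This stands in part: many will enter 1. It does not show that all will.

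Nor is the card the source record. The data come from review plus interview, participants are trained on the card, staff can edit entries (the card has a box for this), and there are examinations and telephone contacts. The recall sentence in section 8.1.1.1 says how missing data are handled and does not limit the interview. This also stands, and it is why no lasting bias can be asserted. What remains is that no rule has staff query a 0.

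Redness and hardness are entered in centimetres, and section 2.2.3.5 describes patch reactions mainly as erythema and papules. The leading sign of the dmLT patch therefore largely escapes the problem.

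A reader might go further and infer that solicited reactions are under-counted, or that comparisons between regimens lose a definite amount of power. The documents support neither. They give no misrecording rate, and section 7.2.2 states that the study was not designed to detect safety differences. The 65% local-reaction figure in section 2.2.3.1 is a share of participants in a multi-dose trial, not a per-dose rate, so it is no basis for a per-dose estimate.

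**Conclusion.** The wording is ambiguous at the point where a reaction is or is not counted, and it touches a primary endpoint. Non-measured mild reactions may be under-recorded, by an amount the documents cannot give. The illustration rests wholly on the assumed share s and on no recovery at review; at s = 0 the effect is nil. Whether the card departs from the DAIDS table cannot be judged here, since its definitions are not reproduced. No sample size or stated probability changes. This is a cheap improvement worth making because entries already collected cannot be fully repaired, not evidence that the safety results would be wrong.

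**What to change.** In Appendix I, reword two levels:

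- 0 = None: symptom not present;
- 1 = Mild: symptom present, with no or only minimal interference, the rest of the descriptor as it stands.

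Leave levels 2 and 3 unchanged. Check the wording against the DAIDS grading table that section 8.1.7 names, and use it in the diary-card training that section 8.1.1.1 already requires. While the card is open, reconcile the swelling item with section 8.1.1.1, which calls for a measured largest dimension.

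The cost is a reprinted card and a line in the training. Recorded rates of mild reactions may come out slightly higher.

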APPENDIX M. ROLES AND RESPONSIBILITIES

Roles and Responsibilities

Protocol Chair:

Responsible for study design and serving as a liaison between the site, the vaccine developers including the Sponsor, and contributing support to overall project management and the analysis and reporting of study data. The chair will support the site PI with clinical trial guidance, protocol preparation, protocol review and response to regulatory reviews. The Chairs do not have contact with study subjects.

Protocol Co-Chair:

Responsible for study design and serving as a liaison between the site and the vaccine developers including the Sponsor and contributing support to overall project management and the analysis and reporting of study data. The Co-Chair will provide support with clinical trial guidance, protocol preparation, protocol review and response to regulatory reviews. The Chairs do not have contact with study subjects.

Principal Investigator:

Responsible for all aspects of the study at the site including performing briefing, consenting, and all other participant interactions, while maintaining the blind.. The principal investigator is the primary person responsible for individual participant safety.

Associate Investigators at the Site:

Assist the Protocol Chairs and Principal Investigators in performing briefing, consenting, and all other participant interactions under their supervision, while maintaining the blind. Site associate investigators can act in place of the PI, if necessary.

Associate Investigators at MHRP:

Assist the Protocol Chairs and will not have contact with study subjects or identifiers.

Laboratory Investigators:

Responsible for laboratory analysis. Lab investigators will not have contact with study subjects or identifiers.

Protocol Statistician:

Responsible for statistical analysis for this study. The protocol statistician will not have contact with study subjects.

Overall Study Pharmacist:

The qualified pharmacist with responsibility for overseeing the import, distribution, inventory, and accountability of vaccine, communication with sponsor/MHRP regarding pharmacy related issues, training and consultation with the study site pharmacy personnel.

Protocol Data Management:

Responsible for data management for this study. The data management team will not have contact with study subjects.

DAIDS Medical Officer:

Responsible for protocol development and liaison for the submission to the DAIDS Clinical Sciences Review Committee review The DAIDS medical officer will not have contact with study subjects or identifiers.

DoD Research Monitor:

The DoD Research Monitor may perform oversight functions (e.g. observe recruitment, enrollment procedures, and the consent process for participants; oversee study interventions and interactions; review monitoring plans and UPIRTSO reports; oversee data collection, and analysis) and report their observations and findings to the IRB. The DoD research monitor may discuss the research protocol with the investigators, interview participants, and consult with others outside of the study about the research. The research monitor shall have authority to stop a research protocol in progress, remove individual participants from a research protocol, and take whatever steps are necessary to protect the safety and well-being of participants until the IRBs can assess the monitor's report. Research Monitors shall have the responsibility to promptly report their observations and findings to the IRB. The DoD Research Monitor is required to review all unanticipated problems involving risks to subjects or others, serious adverse event (SAE) reports, and all participant deaths. The DoD Research Monitor at a minimum must comment on the outcomes of the event or problem and in case of a serious adverse event or death, comments on the relationship to participation in the study. They must also indicate whether he/she concurs with the details of the report provided by the PI.

APPENDIX O. LIST OF PIMMCs

List of Potentially Immune-Mediated Medical Conditions

Gastrointestinal

- Celiac disease
- Crohn's disease
- Ulcerative colitis
- Ulcerative proctitis

Liver

- Autoimmune cholangitis
- Autoimmune hepatitis
- Primary biliary cirrhosis
- Primary sclerosing cholangitis
- Metabolic diseases
- Addison's disease
- Autoimmune thyroiditis (including Hashimoto thyroiditis)
- Diabetes mellitus type I
- Grave's or Basedow's disease

Musculoskeletal

- Dermatomyositis, Polymyositis and Antisynthetase Syndrome
- Juvenile chronic arthritis (including Still's disease)
- Mixed connective tissue disorder
- Polymyalgia rheumatic
- Psoriatic arthropathy
- Relapsing polychondritis
- Rheumatoid arthritis
- Scleroderma, including diffuse systemic form and CREST syndrome
- Spondyloarthritis, including ankylosing spondylitis, reactive arthritis (Reiter's Syndrome) and undifferentiated spondyloarthritis
- Systemic lupus erythematosus

- Systemic sclerosis

Neuroinflammatory:

- Acute disseminated encephalomyelitis, including site specific variants (e.g., non-infectious encephalitis, encephalomyelitis, myelitis, radiculomyelitis)
- Cranial nerve disorders, including paralyses/paresis (e.g., Bell's palsy)
- Guillain-Barré syndrome, including Miller Fisher syndrome and other variants
- Immune-mediated peripheral neuropathies and plexopathies, including chronic inflammatory demyelinating polyneuropathy, multifocal motor neuropathy and polyneuropathies associated with monoclonal gammopathy
- Multiple sclerosis
- Narcolepsy
- Optic neuritis
- Transverse myelitis
- Myasthenia gravis, including Eaton-Lambert syndrome

Skin:

- Alopecia areata
- Autoimmune bullous skin diseases, including pemphigus, pemphigoid and dermatitis herpetiformis
- Cutaneous lupus erythematosus
- Erythema nodosum
- Morphoea
- Lichen planus
- Psoriasis
- Rosacea
- Sweet's syndrome
- Vitiligo

Vasculitides:

- Large vessels vasculitis including: giant cell arteritis such as Takayasu's arteritis and temporal arteritis
- Medium sized and/or small vessels vasculitis including: polyarteritis nodosa, Kawasaki's disease, microscopic polyangiitis, Wegener's granulomatosis, Churg–Strauss syndrome (allergic granulomatous angiitis), Buerger's disease thromboangiitis obliterans, necrotizing vasculitis and anti-neutrophil cytoplasmic antibody (ANCA) positive vasculitis (type unspecified), Henoch–Schonlein purpura, Behcet's syndrome, leukocytoclastic vasculitis

Other:

- Antiphospholipid syndrome
- Asthma and other immune-based lung diseases such as idiopathic pulmonary fibrosis, BOOP
- Autoimmune hemolytic anemia
- Autoimmune glomerulonephritis (including IgA nephropathy, glomerulonephritis rapidly progressive, membranous glomerulonephritis, membranoproliferative glomerulonephritis, and mesangioproliferative glomerulonephritis)
- Autoimmune myocarditis/cardiomyopathy
- Autoimmune thrombocytopenia
- Goodpasture syndrome
- Pernicious anemia
- Raynaud's phenomenon* note: Up to 10% of healthy female population has this without ever developing an autoimmune disease
- Sarcoidosis
- Sjögren's syndrome
- Stevens-Johnson syndrome
- Uveitis

APPENDIX Q. TELEPHONE VISIT SCRIPT

Telephone Visit Script

Site staff may use the telephone script as guidance when carrying out a phone call visit.

- 1) If you reach the participant:
 - a) Introduce yourself.
 - b) Ask if this is a good time for the participant to talk. If so, proceed. If not, try to ascertain a better time to call the participant back.
 - c) State why you are calling with the following: "I am calling to see how you are doing since you received the vaccination"
 - d) If the participant is silent or says something unrevealing such as "Everything is fine, ask the following: "Have you had any complaints?" OR "Are you able to carry out your daily activities without a problem?"
 - e) If the participant identifies a symptom, try to take further history and, based on your judgement, provide remedy, or invite the participant to the clinic for further assessments. Participants with symptoms assessed to be grade 3 and above should be invited for further assessment at the clinic.
 - f) If the participant identifies no symptoms; finish the call with a brief summary, such as "Thank you for your time and I would like to request that you continue filling the diary card and remember to come for your next appointment on the date that you were provided."
 - g) If the participant had a sign or symptom, and you want to evaluate the participant at the clinic, remind he/she to come to the clinic at the earliest opportunity.
- 2) If you do not reach the participant and reach someone else or if connected to voice mail:
 - a) Introduce yourself.
 - b) If you reach someone else, ask if that person knows the participant and request that the participant calls back or ask the best time to call back to talk to the participant.
 - c) In case of voicemail, leave a message for the participant to call back.
 - d) Once the participant is reached, go through the procedure 1 and 2.
- 3) Document the participant's responses and your recommendations, if any, and attempts to contact the participant including time and date.

